### 2.3 ADVERSE EVENTS

Adverse events will be reported on the case report form. Prior to randomisation only grade 3 and 4 adverse events and Serious Adverse Events (SAE) are collected. Post-randomisation, all adverse events will be reported including grade 1 and 2 events, and other notable events (see below).

All clinical events reported during the trial will be reviewed by the Trial Physician (unblinded). Adverse events will be classified by system organ class and lower level term according to the version of MedDRA® implemented at the start of the trial (version 19; the same version will be used throughout).

Adverse events (clinical and laboratory) will be graded using the 2004 (amended 2009) Division of AIDS toxicity grading table (see Appendix III of RIVER protocol).

Serious adverse events will be defined according to principles of GCP.

Other notable events, to be reported on designated CRFs: Vaccine-related events (see Appendix IV of the RIVER protocol), Cancer, Pregnancy in a partner.

Solicited adverse events following the receipt of each vaccine will be recorded on a CRF during the first 60 mins by clinical staff, and then daily by the participant on a diary card for 3 days.

### 2.4 COUNTING OF EVENTS

SAEs will be analysed as episodes, with all components of the same clinical SAE presented as one episode. Analyses of grade 3 or 4 AEs will consider each graded component as separate events. All SAEs are also reported as adverse events; all grade 4 adverse events are reported as SAEs (life-threatening by definition).

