**Table 6 Definitions**

TERM	DEFINITION
Adverse Event (AE)	Any untoward medical occurrence in a participant or clinical study subject to whom a medicinal product has been administered including occurrences that are not necessarily caused by or related to that product.
Adverse Reaction (AR)	Any untoward and unintended response to an investigational medicinal product related to any dose administered.
Unexpected Adverse Reaction (UAR)	An adverse reaction, the nature or severity of which is not consistent with the information about the medicinal product in question set out in the Summary of Product Characteristics (SmPC) or Investigator Brochure (IB) for that product.
Serious Adverse Event (SAE) or Serious Adverse Reaction (SAR) or Suspected Unexpected Serious Adverse Reaction (SUSAR)	Respectively any adverse event, adverse reaction or unexpected adverse reaction that: 
 
▪ Results in death
 
▪ Is life-threatening+++
 
▪ Requires hospitalisation or prolongation of existing hospitalisation§§§
 
▪ Results in persistent or significant disability or incapacity
 
▪ Consists of a congenital anomaly or birth defect
 
▪ Is another important medical condition****
 

+++ The term life-threatening in the definition of a serious event refers to an event in which the participant is at risk of death at the time of the event; it does not refer to an event that hypothetically might cause death if it were more severe, for example, a silent myocardial infarction.

§§§ Hospitalisation is defined as an inpatient admission, regardless of length of stay, even if the hospitalisation is a precautionary measure for continued observation. Hospitalisations for a pre-existing condition, that has not worsened or for an elective procedure do not constitute an SAE.

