\*\*\*\* Medical judgement should be exercised in deciding whether an AE or AR is serious in other situations. The following should also be considered serious: important AEs or ARs that are not immediately life-threatening or do not result in death or hospitalisation but may jeopardise the subject or may require intervention to prevent one of the other outcomes listed in the definition above; for example, a secondary malignancy, an allergic bronchospasm requiring intensive emergency treatment, seizures or blood dyscrasias that do not result in hospitalisation or development of drug dependency.

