## 7.4 INVESTIGATOR RESPONSIBILITIES

All non-serious AEs and ARs, whether expected or not, should be recorded in the participant's medical notes and dependent on what stage of the study the participant has reached may need to be reported to the RIVER Co-ordinating Centre:

- Participants in Cohort I – Recently diagnosed will be on cART alone for 22 weeks prior to randomisation. During this period, prior to randomisation, only grade 3 and 4 adverse events need to be reported on study CRFs.
- From randomisation up until the participant's last study visit (PR18), in addition to grade 3 or 4 events, **all** non-serious AEs and ARs, whether expected or not, should also be recorded in the participant's medical notes and reported on the relevant study CRF.
- Adverse events should be sent to the RIVER Co-ordinating Centre within the agreed timescale of **7 days** from awareness of the event.
- SAEs, SARs and Notable Events should be notified to the RIVER Co-ordinating Centre within **24 hours** of the investigator becoming aware of the event.

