### 7.4.1 INVESTIGATOR ASSESSMENT

#### 7.4.1.A SERIOUSNESS

When an AE or AR occurs, the investigator responsible for the care of the participant must first assess whether or not the event is serious using the definition given in [Section 7.1](#). If the event is serious, then an SAE Form must be completed and the RIVER Co-ordinating Centre notified within 24 hours.

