#### 7.4.1.B SEVERITY OR GRADING OF ADVERSE EVENTS

The severity of all AEs and/or ARs (serious and non-serious) in this study should be graded using the toxicity grading table in [Appendix III](#).

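### SAP 2.4 makes every grade 4 adverse event a life-threatening SAE, a rule the current protocol does not contain; SAE status and type should follow Table 6

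*SAP*

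**What the plan says.** **SAP.** Section 2.4 says that "all grade 4 adverse events are reported as SAEs (life-threatening by definition"). Section 2.3 gives a different basis and mentions no grade: "Serious adverse events will be defined according to principles of GCP". Section 4.8 analyses SAEs overall and by type, life-threatening being one type. It lists grade 3 or 4 adverse events as a separate outcome.

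**Protocol.** The footnote to Table 6 says that life-threatening "refers to an event in which the participant is at risk of death at the time of the event", and that "it does not refer to an event that hypothetically might cause death if it were more severe". The footnote on other important medical conditions says: "Medical judgement should be exercised in deciding whether an AE or AR is serious in other situations". Section 7.4.1.A says the investigator "must first assess whether or not the event is serious using the definition given in" Section 7.1. Section 7.4.1.B treats grading as a step of its own: "The severity of all AEs and/or ARs (serious and non-serious) in this study should be graded using the toxicity grading table in" Appendix III. Section 7.4 opens by referring to non-serious events. It then says that for Cohort I before randomisation "only grade 3 and 4 adverse events need to be reported on study CRFs".

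**The concern.** The two documents use different tests for the same label. The protocol asks whether the participant was in danger at the time. SAP 2.4 asks only what grade the event had. Because clinical and laboratory events are both graded (protocol 6.3, SAP 2.3), an event could reach grade 4 on a measured value without meeting the protocol's test.

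SAP 4.8 presents post-randomisation adverse events by arm and compares them as binary outcomes, so the choice of test can change reported numbers. In a trial of this size a few events are enough to alter how an SAE table reads. If the rule is not applied and the SAE forms are used instead, the SAP asserts an equivalence that the data may not show, and the analyst has no stated way to resolve the difference.

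**Working it through.** The plan gives no figure to reproduce, because neither document states an expected number of grade 4 events. The check is a comparison of definitions, followed by arithmetic on what a difference would do.

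**1. Does any protocol criterion for seriousness refer to grade?** Table 6 lists death, life-threatening, hospitalisation, disability, congenital anomaly and other important medical condition. None is defined by grade.

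**2. Does the protocol apply a grade 4 rule elsewhere?** In Section 7.4, adverse events are due within 7 days. The 24-hour list names SAEs, SARs and notable events, and grade 4 events are not on it. Section 6.3 lists grade 3 and 4 events and SAEs as separate categories. The current body text therefore holds no automatic rule.

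**3. What does the SAP rule do to each kind of grade 4 event?**

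| Grade 4 event | Under protocol Table 6 | Under SAP 2.4 | Difference |
|---|---|---|---|
| A: participant at actual risk of death | SAE, life-threatening | SAE, life-threatening | none |
| B: serious for another reason only (for example hospitalisation, or important by judgement) | SAE of that type | SAE, life-threatening | type wrong, total unchanged |
| C: meets no criterion | not an SAE | SAE, life-threatening | total and type both wrong |

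In counts of events:

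- SAE total under SAP 2.4 − SAE total under Table 6 = C
- life-threatening under SAP 2.4 − life-threatening under Table 6 = B + C

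Both differences are zero or positive, so the rule can only inflate these rows. B and C are not given in the documents.

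**4. Scale per participant.** Section 9.3 of the protocol plans 60 enrolled and bases power on 52, which is 30 or 26 per arm at 1:1. One participant moved from no SAE to an SAE changes the arm's proportion by 1/30 = 3.3 or 1/26 = 3.8 percentage points.

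**5. Illustration with assumed counts.** Suppose no participant in either arm has an SAE under Table 6, and *k* participants in one arm only are reclassified. Two-sided Fisher exact p-values are:

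| *k* | 26 per arm | 30 per arm |
|---|---|---|
| 0 | 1.00 | 1.00 |
| 1 | 1.00 | 1.00 |
| 3 | 0.24 | 0.24 |
| 5 | 0.051 | 0.052 |
| 6 | 0.023 | 0.024 |

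These counts are assumptions, chosen to show sensitivity. They do not predict what the trial will observe.

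**The case against.** Several points count against a stronger reading.

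- **Laboratory events.** A reader might infer that a grade 4 laboratory result without symptoms is never an SAE under the protocol. The documents do not support that. The Table 6 footnote gives blood dyscrasias without hospitalisation as an example of what may be serious. Such an event would be an SAE of another type (case B), so only its life-threatening label would be wrong. Judgement is still required, so this does not make all grade 4 events serious.
- **The grading table.** Appendix III is not in the text available. The only grade 4 definition shown, for QTc in protocol 1.1.1.B, does require life-threatening consequences. If every grade 4 definition were like that, B and C could be empty. The point therefore rests on how the protocol defines and assesses seriousness, and not on any laboratory threshold.
- **Section 7.4.** Its opening words place grade 3 and 4 events under non-serious reporting. The next bullet, however, mentions grade 3 or 4 events alongside non-serious events as if they were distinct. Entry on an ordinary CRF also does not rule out an SAE form, since SAP 2.4 says all SAEs are reported as adverse events too. Section 7.4 supports the point but would not carry it alone.
- **Reporting or derivation.** SAP 2.4 may describe how sites report and not instruct the analyst to reclassify. Even so, it sits in the section on counting events and fixes a type that 4.8 tabulates. A cautious reporting convention would not make an event life-threatening.
- **Direction.** A reader might infer that added events would fall mainly in Arm B, because the protocol describes vorinostat effects on blood results. That is plausible but not established: the effects described come largely from daily dosing in cancer patients, and the protocol expects less frequent dosing may limit toxicity.
- **Amendment log.** The entry for protocol version 2.0 does make grade 4 events reportable as SAEs. It describes superseded text and cannot support the rule now. It may explain where the SAP sentence came from.

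**Conclusion.** The inconsistency is real and lies in the current text of both documents. SAP 2.4 asserts an equivalence that protocol Table 6 and Section 7.4 do not contain and that does not follow from SAP 2.3. Applied as written, it over-counts SAEs by C and the life-threatening type by B + C.

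The size is unknown and may be zero, so it would be too strong to say that the SAE tables will be misstated. The conclusion is conditional: they are misstated whenever a grade 4 event fails Table 6 or is serious only for a reason other than risk of death. It assumes that the analyst applies SAP 2.4 as written and that investigators judge seriousness by Table 6. This is a minor point confined to safety reporting. The primary endpoint, its analysis and the sample size are untouched.

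**What to change.** Remove the automatic equivalence from SAP 2.4. State in its place that SAE status and SAE type in the 4.8 tables come from the investigator's assessment against protocol Table 6, as recorded on the SAE form. Non-serious grade 4 events then appear only in the grade 3 or 4 analysis, which SAP 4.8 already plans, so no new table is needed.

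Before making the edit, check the site instructions and SAE forms. If the intention is that sites report all grade 4 events as SAEs, protocol Section 7.4 and SAP 2.4 must say so consistently, and the life-threatening type should still follow Table 6.

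The cost is one SAP sentence in the first case. In the second it is that sentence plus a matching clarification in the protocol. Neither needs new data collection.

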### 2.5 OTHER DEFINITIONS

Glomerular filtration rate will be estimated by Chronic Kidney Disease Epidemiology Collaboration (CKD-EPI) creatinine based GFR estimating equation [1].

### 3 ANALYSIS PRINCIPLES

- The trial will be primarily analysed as intention-to-treat including all randomised participants. Based on the consideration that the trial is evaluating the efficacy, as measured by the impact on total CD4+ HV DNA of a novel intervention, sensitivity analyses will also be performed for immunological/virological outcomes excluding participants with incomplete intervention (temporary/complete stop of ART, vaccination, or vorinostat).
- Randomisation arms will be compared using data between baseline and the post-randomisation week 18 visit (inclusive). Data collected in the period between enrolment and randomisation will be reported for stratum I as baseline data.
- For continuous variables, the following will be presented by scheduled visits and by randomised group:
  - number of participants with a measurement
  - mean (SD) or median (IQR) of absolute values and of changes in absolute values from baseline
  - mean changes (plus point-wise 95% CI) from baseline in each randomised group, calculated using normal regression of absolute values, adjusting for the baseline measurement.
  - normal generalized linear regression models (using GEE) will be used for a global test of difference between treatment groups across all visits

If positively skewed, data will be log-transformed before the analysis. If parametric models/tests do not seem to be appropriate, rank tests will be performed.

- Binary and categorical variables will be tabulated, overall and by randomised group. Differences between groups at particular time-points will be tested using chi-squared tests (or exact tests if appropriate), and logistic regression models for adjusted analyses. GEE models will be used for a global test of difference between treatment groups across all visits.
- Time-to-event outcomes will consider time from baseline to the event date, using Kaplan-Meier estimation. For participants who have not reached the event in question, the date of last clinic visit will be used as a censoring time. Differences between groups in time-to-event outcomes will be tested using a log-rank test and Cox proportional hazard regression models (stratified by the stratification factors).
- Primary analyses will be adjusted for membership of stratum I versus stratum II; secondary analysis will be conducted without adjustment.
- Multiple imputations will be performed to account for missing data in the primary outcome measure (see below). Analyses of secondary endpoint, unless otherwise stated, will be based on available data only. Reasons for missing efficacy data will be described.
- All estimates including differences between randomised groups will be presented with a 2-sided 95% confidence interval. All statistical tests will be 2-sided. P values will be given to 2 decimal places if  $\geq 0.10$ , otherwise to 1 significant figure.

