#### **6.4 PROCEDURES FOR ASSESSING QUALITY OF LIFE**

All participants will be asked to complete the EQ-5D-5L questionnaire at enrolment (visit only applicable to Cohort I – Recently diagnosed), randomisation, post-randomisation week 08 day 3 (PR08-3) and the final visit, post-randomisation week 18 (PR18). ([Appendix X](#)).

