## 1.4 SAMPLE SIZE

The sample size calculation is based on the primary endpoint which will be analysed on a  $\log_{10}$ -scale. The following assumptions are made:

- The combination intervention will confer a 50% reduction in total HIV DNA when compared with cART alone. On a  $\log_{10}$ -scale this corresponds to a difference between the two arms of  $\log_{10}(2)$  (approximately 0.3). The effect is assumed to be the same in both strata (recently and previously diagnosed patients).
- Standard deviation (SD) is 0.4 for a single measurement in both arms based on two publications:
  - Reported on data from 31 participants treated with HAART at PHI in the French PRIMO study. The median (IQR) at 6 and 12 months after starting treatment were 2.30 (2.10, 2.70) and 2.10 (1.80, 2.40)  $\log_{10}$  DNA copies/ $10^6$  PBMC respectively suggesting a SD of 0.45 at both time points.
  - Reported on 8 participants with PHI. At week 52, the median (IQR) was 494 (250 - 694) for total HIV-1 DNA copies/ $10^6$  CD4+ T-cells suggesting a SD (in log scale) of 0.33.
- 1:1 allocation of participants in the two study arms.
- Method of analysis: comparing the treatment arms in terms of absolute HIV total DNA level at post-randomisation weeks 16 and 18 adjusted for baseline (here: randomisation) level (analysis of covariance; ANCOVA); one baseline measurement and two follow-up measurements (at PR16 and 18) will be taken for an individual participant.
- A correlation coefficient of 0.5 between a baseline measurement and a PR 16/18 measurement, and a correlation coefficient of 0.7 for measurements at PR 16 and 18.
- Two-sided  $\alpha = 0.05$  for the null hypothesis that there is no difference between the two arms in the primary endpoint.

Under the above assumptions, a sample size of 52 individuals would provide 94% power to detect a 50% reduction in HIV total DNA (86% power for a 45% reduction).

Assuming that some individuals enrolled will not reach visits PR 16/18 (due to failing the eligibility criteria for randomisation in stratum I, or withdrawal) it is planned to enrol a total of 60 individuals overall (both strata combined).

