## 4.7 SECONDARY ENDPOINTS: EFFICACY

- HIV integrated DNA:**

Measurements (copies/million CD4+T cells) at enrolment (in recently infected patients), baseline, PR week 08-3, PR week 12-2, PR week 16, and PR week 18.

Analysed as for continuous outcomes as specified above. Treatment arms will be compared in terms of absolute integrated HIV DNA levels at post-randomisation weeks 16 and 18 adjusted for the baseline level and by stratum.

- Plasma HIV RNA measured with an ultra-low copy assay:**

Number (%) with undetectable HIV-RNA at enrolment (in recently infected patients), baseline, PR week 08-3, PR week 09-2, PR week 12-2, PR week 16, and PR week 18; analysed as for binary outcomes as specified above.

- **Replication competence (Viral Outgrowth assay):**

Measurements (infectious units per million cells; IUPM) at baseline and PR week 16. Analysed as for binary and continuous outcomes as specified above. The results are expected to be “negative” (i.e. below the lower limit of detection) in a sizable proportion of samples. Therefore, the treatment arms will be compared as follows:

- 1) Primary analysis:
  - a) Comparison of the proportion of patients with a “negative” result using logistic regression. This analysis includes all patients with a valid PR-16 result.
  - b) Comparison of IUPM in patients with “positive” results using median regression. Patients with a “negative” PR-16 result will be excluded.
- 2) Secondary analysis:  
Comparison of IUPM using a linear model appropriate for left-censored data. This analysis includes all patients with a valid PR-16 result, “positive” or “negative”.

In all analyses, patients with missing PR-16 samples or invalid PR-16 results (due to assay failure) will be ignored. Analyses will be adjusted for stratum and baseline viral outgrowth. Missing baseline values will be imputed; predictors may include stratum, and other factors associated eg CD4, HIV-DNA.

- **HIV-specific T cell responses (both CD8+ and CD4+ T cell responses):**

Measurements using intracellular cytokine staining (ICS) at enrolment (in recently infected patients), baseline, PR week 09-2, PR week 12-2, and PR week 16. For both CD8+ and CD4+ T cells, the following markers will be measured: CD107a+, CD154+, IFNg+, IL2+, and TNFa+.

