For each marker, the magnitude of a response is defined as the number of positive cells as percentage of their parental populations, after subtracting the negative control. For technical reasons, HIV antigens will be divided in non-overlapping pools values for each sample; responses will be added up for each marker.

At each time-point, the magnitude of responses, and the change from baseline will be analysed as for continuous outcomes as specified above.

- **CD8+ T cell antiviral activity (viral inhibition)**

Measurements using a flow cytometer-based assay [2] at enrolment (in recently infected patients), baseline, PR week 09-2, PR week 12-2, and PR week 16.

CD8+ T cell antiviral suppressive activity will be expressed as percentage inhibition and determined as follows:  $\frac{[(\text{fraction of p24} + \text{cells in CD4} + \text{T cells cultured alone}) - (\text{fraction of p24} + \text{in CD4+ T cells cultured with CD8+ cells})]}{(\text{fraction of p24} + \text{cells in CD4} + \text{T cells cultured alone})} \times 100$ .

CD8+ T cell antiviral suppressive activity will be analysed as described above for continuous outcomes.

- **Inflammatory biomarkers:**

For example CD4:8 ratio, immune exhaustion/activation markers, IL-6 and d-dimer, neuro-inflammation markers. Analysed as for continuous outcomes as specified above.

- **HIV cell associated RNA (arm B only):**

Measurements (copies/million 18S copies) pre and 2 hours post vorinostat at visits PR week 08-3, PR week 09-2, and PR week 12-2. Comparison of pre and post vorinostat values will be performed using paired t-tests (or paired rank-tests if appropriate).

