#### 4.9 OTHER ENDPOINTS

The following variables will be analysed as for continuous outcomes as specified above:

- CD4 (cells/mm^3), CD4:CD8 ratio
- Quality of Life: summary score

In addition, the following will be presented over scheduled visits:

- Suppressed HIV-RNA: number (%)
- QTc interval  $\leq$ 440ms: number (%)
- eGFR $<$ 60 ml/min/1.73m^2: number (%)
- Platelet count  $\geq$ 150x10^9/L: number (%)
- Low haemoglobin (Hb $\geq$ 12g/dL for males,  $\geq$ 11g/dL for females): number (%)
- ALT  $<$ 5xULN
- Merck p24 assay: To be specified.

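### Do the GEE global tests of secondary outcomes need a stated variance estimator and small-sample rule with 52 to 60 participants?

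*SAP*

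**What the plan says.** SAP section 3 sets general rules that later sections call on. For continuous variables, besides per-visit regressions adjusted for baseline, "normal generalized linear regression models (using GEE) will be used for a global test of difference between treatment groups across all visits". For binary and categorical variables, "GEE models will be used for a global test of difference between treatment groups across all visits". Neither sentence goes further. Section 3 also has positively skewed data log-transformed, allows rank tests where parametric methods look unsuitable, and allows exact tests for binary comparisons at particular time-points. None of these concerns the GEE variance.

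On size, SAP 1.4 bases power on 52 participants and adds that "it is planned to enrol a total of 60 individuals overall (both strata combined").

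Three outcomes with several post-baseline visits come under these rules without narrower wording:

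- CD8+ viral inhibition, three visits (SAP 4.7): "CD8+ T cell antiviral suppressive activity will be analysed as described above for continuous outcomes".
- Quality of life (SAP 4.9): "Quality of Life: summary score", collected after randomisation at "post-randomisation week 08 day 3 (PR08-3) and the final visit, post-randomisation week 18 (PR18"), so two visits.
- Ultra-low copy plasma RNA, binary, five visits (SAP 4.7), ending "PR week 12-2, PR week 16, and PR week 18; analysed as for binary outcomes as specified above".

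Others are open. For the T-cell responses, "At each time-point, the magnitude of responses, and the change from baseline will be analysed as for continuous outcomes as specified above" may mean only the per-visit regressions. Integrated DNA has its own comparison at weeks 16 and 18. Inflammatory biomarkers have no visits listed.

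**The concern.** The usual GEE sandwich variance is justified for many independent clusters. Here the clusters are participants, 26 to 30 per arm. In samples of that size the uncorrected sandwich is too small on average, and a chi-square reference ignores its own sampling error. Both push the Wald test towards rejecting too often, and the excess grows with the number of visits tested jointly. Software defaults differ, so the same data could give different p-values depending on a choice the SAP does not record. A single arm effect and a joint arm-by-visit test also address different hypotheses. In an open-label trial one would like such choices fixed before the data are seen. At stake are false positive signals on immunological, virological and quality-of-life outcomes.

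**Working it through.** **Inputs.** Participants: 52 and 60 (SAP 1.4). Correlations: 0.5 between baseline and follow-up, 0.7 between follow-ups (SAP 1.4, given for total HIV DNA and borrowed here for the secondary outcomes). Nominal level: two-sided 5%, which the SAP states only for the primary endpoint. Post-baseline visits: 2 or 3 for the continuous outcomes that clearly fall under the rule (SAP 4.7, 4.9; Protocol 6.4).

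**The plan's own figure first.** Residual SD for the mean of two follow-ups, adjusted for baseline: 0.4 × √[(1 + 0.7)/2 − 0.5²] = 0.4 × √0.60 = 0.3098. Standard error of the arm difference with 26 per arm: 0.3098 × √(2/26) = 0.0859. For a 50% reduction, 0.3010/0.0859 = 3.50, and Φ(3.50 − 1.96) = 93.9%. For 45%, 0.2596/0.0859 = 3.02, and Φ(3.02 − 1.96) = 85.6%. The stated 94% and 86% reproduce. The documents give no error rate for the GEE tests.

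**Closed form, no covariates.** With complete normal data, equal arms, and visit and arm terms only, the uncorrected sandwich Wald statistic is W = T² × n/(n − 2), where T² is the ordinary two-sample statistic on n − 2 degrees of freedom (Hotelling's for a joint test). Rejecting when W exceeds the chi-square critical value c on q degrees of freedom therefore means rejecting when F(q, n − 1 − q) exceeds c × (n − 1 − q)/(n × q).

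- Single effect, n = 52: 3.841 × 50/52 = 3.694 on (1, 50), error 6.0%. For n = 60: 3.841 × 58/60 = 3.713 on (1, 58), error 5.9%.
- Joint, 2 visits, n = 52: 5.991 × 49/(52 × 2) = 2.823 on (2, 49), error 6.9%. For n = 60: 5.991 × 57/(60 × 2) = 2.846 on (2, 57), error 6.6%.
- Joint, 3 visits, n = 52: 7.815 × 48/(52 × 3) = 2.405 on (3, 48), error 7.9%. For n = 60: 7.815 × 56/(60 × 3) = 2.431 on (3, 56), error 7.5%.

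These do not depend on the SD or the correlations. Simulation of the same model gave 5.9 and 6.0% (single effect, 3 visits), 7.0 and 6.5% (joint, 2 visits), and 7.8 and 7.5% (joint, 3 visits), for n = 52 and 60 respectively.

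**Simulation with baseline and stratum in the model.** No true effect, 20,000 trials per cell, Monte Carlo standard error about 0.2 points. Error rates in %:

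| n | Visits | Single, uncorrected | Single, df-corrected F | Joint, uncorrected | Joint, df-corrected F |
|---|---|---|---|---|---|
| 52 | 2 | 6.5 | 5.0 | 7.7 | 4.9 |
| 52 | 3 | 6.8 | 5.1 | 8.2 | 4.5 |
| 60 | 2 | 6.3 | 5.0 | 6.9 | 4.6 |
| 60 | 3 | 6.2 | 4.8 | 7.8 | 4.7 |

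A robust score test gave 5.3 to 5.7% (single) and 5.0 to 5.6% (joint). The highest uncorrected joint figure at two or three visits, 9.0%, needs a baseline-by-visit term, n = 52 and three visits.

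**Separately coded simulation, same setting.** Uncorrected sandwich: 6.0 to 6.6% (single) and 6.9 to 7.8% (joint). Model-based variance with exchangeable working correlation: 4.6 to 6.4%. Sandwich with only an F reference: 5.5 to 6.3%.

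The inflation is thus real under one way of carrying out the test, and mostly absent under several other ordinary ways.

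**The case for a change.** The best case for a change is that the unstated choices can move the error rate a long way. Model-based variance with an independence working correlation gives a single-effect error of 12.5 to 13.0% at two visits and 17.0 to 19.8% at three. For the five-visit binary outcome, an uncorrected joint test reached 10.5 to 16.3% at a latent correlation of 0.8. A joint test of integrated DNA over its four visits would run at 8.6 to 9.4%. The SAP shows, in its viral outgrowth paragraph, that it can specify models closely, and two or three more sentences would cost almost nothing.

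Part of this stands. The omission is real, and single effect versus joint test is a genuine choice of hypothesis. The large figures do not carry the argument. Model-based independence variance ignores within-person correlation, which defeats the reason for using GEE, and nothing in the documents points to it. The binary figures rest on event rates (0.5 to 0.8) and latent correlations (0.3 to 0.8) that the documents do not give. The obvious correction, Kauermann-Carroll with an F reference, itself ranged from 2.4 to 9.8% for that joint test, so writing it into the SAP would not settle the matter. The integrated DNA figure applies only if the comparison the SAP gives at weeks 16 and 18 is set aside.

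**Conclusion.** No change follows. SAP section 3 is silent on these details but states no wrong rule. For continuous outcomes with two or three visits and 52 to 60 participants, an uncorrected sandwich Wald test would run at about 6 to 7% (single effect) or 7 to 8% (joint) instead of 5%. A degrees-of-freedom-corrected F test, a robust score test or model-based exchangeable variance would run at roughly 4.5 to 6.4%. A statistician programming the analysis would be expected to choose among these, and which is best is open to debate.

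The reach is narrow: clearly CD8+ viral inhibition and ultra-low copy RNA, plus quality of life, which the SAP lists under other endpoints. No decision depends on these tests, and p-values below 0.10 are reported to one significant figure. The primary analysis of covariance and the per-visit estimates with their confidence intervals do not change.

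The simulated figures assume complete, normal data and the correlations of SAP 1.4. The secondary analyses will use available data, so the exact rates may differ somewhat. The closed-form check without covariates does not need the correlations and agrees with the simulation.
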